- Official Title: Esthetic Outcomes of a Newly Developed Dental Composite and Adhesive System: a Randomized Clinical Trial
- NCT Number: NCT03716349
- Document Date: May 5, 2025

Objective: The aim of this randomized, split mouth clinical trial is to evaluate and compare the esthetic outcomes and patient satisfaction of a simplified newly developed dental composite system (system A) for the esthetic region to a nanohybrid composite system (Filtek Supreme Ultra-system B) placed in class III, IV and V lesions. Even though dental composite systems have been used extensively for the anterior region, clinicians face challenges with shade selection and longevity of the material over the years. This new system has been developed to improve the esthetic outcomes and patient satisfaction by enhancing the blending capability of the material.

Design: This is a randomized, split-mouth study (*ClinicalTrials.gov identifier-NCT03716349*). The study population consists of adult subjects (ages 18-99) that had one pair of class III, IV, or V lesions necessitating restorations. Subjects cannot have fewer than 20 teeth, rampant/controlled caries activity, bruxism, or undergoing or in need of TMJ therapy, or known allergies to methacrylate-based materials.

Methods: Consented subjects will have two restorations placed in their mouth, one restoration using system A and one restoration using system B. Randomization will be done as 1:1, in which each tooth will a 50% chance of being assigned to the restoration using System A or a 50% chance of being assigned to a restoration using system B. Subjects will voluntarily complete questionnaires at study visits.

Statistical Analysis Plan: For system A and system B, the primary outcome is patient satisfaction of the restoration's appearance using the Visual Analog Scale of 0-100 with 0 being a poor result and 100 being an excellent result, specifically at the 5-year visit. Descriptive statistics, including mean, standard deviation, minimum, maximum, median, and frequency distributions, will be compiled to profile the baseline, 6-month, 12-month, 24-month, 36-month, and 5-year clinical categories (such as retention rate, marginal adaptation, marginal discoloration, etc.) for each material. A paired-sample t-test or a non-parametric Wilcoxon signed-rank test (as the assumption of normality is not valid), a chi-square or Fisher's exact test will be conducted to detect the differences in the ratings of the two materials at the baseline, 6-month, 12-month, 24-month, 36-month, and 5 years. A McNemar's test, a paired-sample t-test or a non-parametric Wilcoxon signed-rank test, and chi-square or Fisher's exact test will be used to evaluate and compare the performance of materials between the baseline and each time period. Moreover, Mixed model or GEE (Generalized Estimating Equation) will be performed to explore the associations between clinical categories such as retention rate and independent variables (time and material). All tests will employ a 0.05 level of statistical significance. SAS for Windows (v9.1, SAS Institute Inc, Cary, NC, USA) will be used

for the data analysis. A continuous outcome time-to-failure survival analysis will also be performed including both censored and uncensored data.

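### Chi-square and Fisher's exact tests are listed for paired split-mouth ratings; this misfits the non-primary categorical outcomes, mainly binary ones such as retention, but not the primary VAS.

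*Combined protocol and SAP*

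**What the plan says.** The Methods paragraph sets the design: "Consented subjects will have two restorations placed in their mouth, one restoration using system A and one restoration using system B". The Design paragraph adds that subjects "had one pair of class III, IV, or V lesions necessitating restorations", and the allocation is by tooth within the mouth ("Randomization will be done as 1:1").

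The Statistical Analysis Plan then has three relevant sentences.

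- **A against B at each of six time points** (baseline, 6, 12, 24 and 36 months, 5 years). A paired t-test or a Wilcoxon signed-rank test is offered, and then "a chi-square or Fisher's exact test will be conducted to detect the differences in the ratings of the two materials". McNemar's test does not appear in this sentence.
- **Baseline against each later visit.** The list opens with "A McNemar's test, a paired-sample t-test or a non-parametric Wilcoxon signed-rank test" and continues: "chi-square or Fisher's exact test will be used to evaluate and compare the performance of materials between the baseline and each time period".
- **Modelling.** "Mixed model or GEE (Generalized Estimating Equation) will be performed to explore the associations" between clinical categories, such as retention, and time and material. No clustering unit or correlation structure is given.

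No rule says which test goes with which variable. The primary outcome is the 0-100 VAS for satisfaction with appearance at 5 years.

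**The concern.** Chi-square and Fisher's exact tests treat the two columns being compared as separate samples. Here they never are. At a visit, the A and B ratings come from the same mouth; over time, the two ratings come from the same restoration. The documents describe no independent groups to which these tests could properly apply.

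For a binary A v B rating, the only tests named specifically for categorical data are therefore the wrong kind. If ratings within a mouth are positively correlated, the unpaired standard error is too large and the split-mouth design loses the precision it was chosen for. When a new material is set against an established one, differences missed in this way can make the two look alike. For change over time, valid and invalid tests stand side by side with nothing to choose between them, so the choice could be made after the data are seen.

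**Working it through.** The documents give no sample size, rates, power or within-pair correlation, so there is no figure of theirs to reproduce. The only stated input is the 0.05 significance level, taken here as two-sided. Everything else below is assumed.

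**1. True size of the unpaired test.** With n pairs, a common rate p and within-pair correlation ρ:

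- true variance of the difference in proportions: 2p(1−p)(1−ρ)/n
- variance used by chi-square: 2p(1−p)/n
- SE overstated by the factor 1/√(1−ρ)
- true two-sided size: 2[1 − Φ(1.96/√(1−ρ))]
- power of the unpaired test where the paired test has 80%: Φ(2.80 − 1.96/√(1−ρ))

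| ρ (assumed) | SE factor | 1.96/√(1−ρ) | True size | Power in place of 80% |
|---|---|---|---|---|
| −0.2 | 0.91 | 1.79 | 7.4% | – |
| 0 | 1.00 | 1.96 | 5.0% | 80% |
| 0.2 | 1.12 | 2.19 | 2.8% | 73% |
| 0.3 | 1.20 | 2.34 | 1.9% | 68% |
| 0.5 | 1.41 | 2.77 | 0.6% | 51% |

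These are large-sample results. The nominal level is right only at ρ = 0.

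**2. Power in a small trial.** Simulated, assuming 40 pairs and non-ideal rates of 15% v 35%; repeat runs agree to within about one percentage point.

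| ρ (assumed) | Fisher | Chi-square | Exact McNemar | Mid-p McNemar |
|---|---|---|---|---|
| 0.2 | 46% | 56% | 53% | 62% |
| 0.3 | 45% | 56% | 58% | 68% |
| 0.5 | 44% | 57% | 75% | 84% |

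With these rates the correlation cannot exceed (0.15 − 0.15×0.35)/√(0.15×0.85×0.35×0.65) ≈ 0.57, so the last row is close to the ceiling.

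**3. One table (hypothetical).** Take 50 pairs: 30 good with both materials, 10 with A only, 2 with B only, 8 with neither.

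- Unpaired: 40/50 v 32/50, pooled 0.72. Chi-square = 0.16²/(0.72×0.28×2/50) = 3.17, p = 0.075. Fisher p = 0.118.
- Paired: McNemar = (10−2)²/(10+2) = 5.33, p = 0.021. Exact p = 2(1+12+66)/4096 = 0.039.

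The within-pair correlation in this table is (30×8 − 10×2)/√(40×10×32×18) = 220/480 = 0.46. On these data the choice of test decides which side of 0.05 the result falls.

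**The case against.** The strongest reply is that the plan already recognises pairing. The A v B sentence offers the signed-rank test for the ratings and does not confine it to continuous scores. That covers ordinal ratings, and on 0/1 data signed-rank reduces to the sign test, which makes the same comparison as McNemar. McNemar is named first for change over time. A mixed model or GEE is planned. The primary VAS has paired tests. Where the unpaired tests err under positive correlation, they err towards caution.

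Most of this stands and sets the limits of the point. A reader might infer that no categorical outcome has a suitable test at any visit; the signed-rank and McNemar entries rule that out. A reader might also infer inflated false positives, or a threat to the primary result. The first would need negative within-mouth correlation, for which the documents give no evidence, and the second is excluded by the paired tests named for the VAS. Nor does the power table show a large gain everywhere: at ρ = 0.2 exact McNemar (53%) is slightly below chi-square (56%), and only mid-p (62%) is ahead.

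What the reply does not remove is that two tests are listed for data they do not fit, with no rule directing the analyst away from them. The mixed model or GEE is exploratory, has no stated clustering, and does not replace the listed tests.

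**Conclusion.** The plan is wrong as written for the non-primary categorical ratings. The clearest case is binary A v B comparisons such as retention, where no McNemar-type test is named. The lesser case is change over time, where the unpaired tests are an unsuitable addition to a list that already holds suitable ones.

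The mismatch between test and design follows from the documents alone. Its size does not. It rests on an assumed correlation and, for the simulated power, on assumed rates and number of pairs. Over correlations of 0.2 to 0.5, true size is 2.8% down to 0.6%, and mid-p McNemar gains about 6 to 27 percentage points of power over chi-square (62−56 and 84−57). Positive correlation is plausible within a mouth but is not established by the documents; at −0.2 the size would be 7.4%. This should be fixed before analysis, but it does not endanger the primary comparison.

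**What to change.** - Remove chi-square and Fisher's exact from both sentences of the Statistical Analysis Plan.
- **Binary ratings**, A v B at each visit and baseline v follow-up within a material: use McNemar, either mid-p or exact, and say which. Exact carries a small power cost at low correlation. Report the paired risk difference with a 95% CI.
- **Ordinal or multi-category ratings**, for both comparisons: use Wilcoxon signed-rank for ordered categories and Stuart-Maxwell or Bowker otherwise.
- Add a short table assigning one test to each variable, so that the choice does not depend on the data.
- State that the mixed model or GEE clusters on subject.

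The cost is a few lines of SAP text and code. No new data and no change to trial conduct are needed.

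### Visit-versus-baseline tests of retention only count losses, and separate tests per material do not compare A with B

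*Combined protocol and SAP*

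**What the plan says.** The Methods paragraph gives each subject "one restoration using system A and one restoration using system B", so the two materials are paired within the mouth. The Statistical Analysis Plan profiles, at baseline and at five later visits, the "clinical categories (such as retention rate, marginal adaptation, marginal discoloration, etc.) for each material". For change over time it says that "A McNemar's test, a paired-sample t-test or a non-parametric Wilcoxon signed-rank test, and chi-square or Fisher's exact test will be used". The purpose it gives for this set of tests is to "evaluate and compare the performance of materials between the baseline and each time period". This is the only place where McNemar's test is named. No test is matched to a category, and no category is excepted.

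The sentence before it covers A against B at baseline and every later visit. It names a paired t-test or Wilcoxon signed-rank test, and says that "a chi-square or Fisher's exact test will be conducted to detect the differences in the ratings of the two materials". A mixed model or GEE with time and material as explanatory variables is also planned. So is a "time-to-failure survival analysis will also be performed including both censored and uncensored data", with no A-versus-B test named for it. On the error level: "All tests will employ a 0.05 level of statistical significance". Sidedness is not stated.

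**The concern.** Retention is the plainest binary category in the list, and McNemar's test is the paired binary test offered for change from baseline, so applying one to the other is the natural reading. But a restoration that has just been placed is retained. If every restoration starts retained, movement is possible only from retained to lost, and the test merely counts losses.

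The trial's question is A against B. A test of visit against baseline run within one material contains no such contrast, yet the sentence speaks of comparing the materials. A report that one system changed significantly from baseline and the other did not could be taken as a difference between systems. What is at stake is the reading of a secondary outcome at up to five follow-up visits.

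**Working it through.** The documents give no sample size, loss rate or power figure, so there is no planned number to reproduce. The check works from the test formulas.

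**Inputs.** Tests and the 0.05 level: Statistical Analysis Plan. Pairing: Methods. Assumed: two-sided testing; all N restorations of a material retained at baseline; a lost restoration is not later counted as retained; N between 20 and 200.

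**Step 1: McNemar against baseline, within one material.** Let b be the number of losses and c the number of gains, with c = 0.
- Exact: p = min(1, 2 × 0.5^b).
- Uncorrected: chi-square = b on 1 df.
- Continuity-corrected: chi-square = (b − 1)²/b on 1 df.

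N appears in none of these.

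**Step 2: Fisher's exact test**, treating baseline and visit as two independent groups of N: p = 2 × C(N, b)/C(2N, b). For N = 20 and b = 5 this is 2 × 15,504/658,008 = 0.047.

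| Losses b | McNemar exact | McNemar corrected | McNemar uncorrected | Fisher N = 20 | Fisher N = 30 | Fisher N = 200 |
|---|---|---|---|---|---|---|
| 3 | 0.250 | 0.248 | 0.083 | 0.231 | 0.237 | 0.248 |
| 4 | 0.125 | 0.134 | 0.0455 | 0.106 | 0.112 | 0.123 |
| 5 | 0.0625 | 0.074 | 0.025 | 0.047 | 0.052 | 0.061 |
| 6 | 0.031 | 0.041 | 0.014 | 0.020 | 0.024 | 0.030 |

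Significance starts at 6 losses for exact or corrected McNemar and at 4 for uncorrected, at any N. For Fisher it starts at 5 losses when N = 20 and at 6 when N = 30, 50, 100 or 200. Thus 6 of 20 lost (30%) and 6 of 200 lost (3%) give the same McNemar p-value.

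**Step 3: two within-material tests against one direct test.** Take 6 losses on A and 5 on B.
- A against baseline: 2 × 0.5^6 = 0.031.
- B against baseline: 2 × 0.5^5 = 0.0625.
- A against B within pairs, no subject losing both: 6 A-only against 5 B-only, exact p = 1.00.
- If m subjects lost both, the discordant counts are 6 − m and 5 − m. Their total, 11 − 2m, is odd, so the upper tail is exactly 0.5 and p = 2 × 0.5 = 1.00 again.

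**Step 4: how often equal materials would split.** Let r be the chance of 6 or more losses out of N. If both materials share the same true loss rate and losses are independent, exactly one is significant by the exact test with chance 2r(1 − r).

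| True loss rate (assumed) | N = 20 | N = 30 | N = 50 | N = 100 |
|---|---|---|---|---|
| 2% | 0.0% | 0.0% | 0.1% | 3.0% |
| 5% | 0.1% | 0.7% | 7.3% | 47.3% |
| 10% | 2.2% | 13.6% | 47.3% | 10.9% |
| 20% | 31.5% | 48.9% | 9.1% | 0.0% |

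For N = 50 at 10%: r = 0.384, and 2 × 0.384 × 0.616 = 0.473. Positive correlation of losses within a mouth would lower these figures.

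**The case against.** The strongest reply is that A against B is already tested. The sentence before plans it at every visit, and the mixed model or GEE includes material, so the baseline tests are supplementary. Reading them as the treatment comparison would be a reporting error that the plan does not prescribe. This stands, and it keeps the point small. It does not justify a test that adds nothing to the loss count, under wording that invites the misreading.

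Four stronger readings are tempting, and the documents do not support them:
- A reader might infer that all clinical categories start perfect. The documents define neither baseline nor a rating scale and give no baseline ratings. Marginal adaptation and discoloration may vary at the start, so the degeneracy is secure for retention only.
- A reader might infer that the null hypothesis is impossible. With gains fixed at zero, the null is a loss probability of zero. That is implausible at 5 years but not excluded, least of all at 6 months.
- A reader might infer that 5 of 20 lost would be non-significant whatever the test. It is for exact McNemar (0.0625), but not for uncorrected McNemar (0.025) or Fisher (0.047), and the plan does not fix the version.
- A reader might infer that the plan has no comparison of the materials. It has several.

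It is also fair to say that change over time within a material is a legitimate descriptive question for graded ratings. The fix keeps it.

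**Conclusion.** The concern holds for retention, as a minor point on a secondary outcome. Tested against a fully retained baseline, McNemar's p-value depends on the loss count alone, and Fisher's varies only slightly with sample size. Neither conveys the loss rate. For any category, separate within-material tests do not compare A with B, as the case of 6 against 5 losses shows.

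This rests on full retention at baseline, which follows from what a newly placed restoration is but is not stated; on two-sided testing; and, for the Fisher cut-offs and the split probabilities, on assumed sample sizes and loss rates. The split probabilities run from near 0 to about 49% over the range shown, so they illustrate the risk and do not predict it. A reader might infer that the trial's main conclusion is at risk. It is not: the degeneracy does not touch the primary outcome, VAS satisfaction at 5 years.

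A related gap makes the repair worthwhile. For binary ratings of A against B, the categorical tests named are chi-square and Fisher, which ignore the split-mouth pairing, while McNemar's test, which would respect it, is named only for change from baseline.

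**What to change.** Amend the Statistical Analysis Plan as follows.

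1. Drop the baseline-versus-visit test for retention, and for any other rating found to be uniformly ideal at baseline.
2. At each follow-up visit, report each material's number of losses, the denominator, and the cumulative loss rate with an exact 95% CI. The interval shows what the p-value hides: 5 of 20 gives 9% to 49%, and 6 of 200 gives 1% to 6%.
3. For binary ratings, test A against B at each visit with a paired method, either McNemar's test on subject pairs (stating exact or asymptotic) or a GEE clustered by subject, in place of the unpaired chi-square or Fisher test.
4. For all other ratings, label within-material change from baseline as descriptive, and state that any conclusion about A against B comes only from a within-subject comparison.

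The cost is SAP wording and the loss of the within-material p-values for retention. No new data are needed.
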